4.6. Schematic Study Diagram

Figure 4-1: Schematic Diagram

4.7. Rationale for study design and selection of dose

4.7.1. Placebo Rationale

EDP1815-207 will utilize a matching placebo control in each cohort in order to fulfill the double-blind design of the study, so that neither the investigator nor subject has knowledge of the treatment being administered. The purpose of this study design is to control for the placebo effect, control for variables caused by knowledge of treatment assignment, control for other factors that can influence study outcomes, and finally to allow for a more complete understanding of the risk-benefit profile of the active study drug. A position statement from the International Eczema Council (Leshem, et al., 2019) has given clear guidance on the design of studies in atopic dermatitis, including supporting and giving a scientific rationale for the use of placebo-control in studies in this condition. Placebo-controlled studies are the recommended standard. In addition, in this study, we are minimizing the proportion of placebo subjects by using a 3:1 randomization ratio (Cohorts 1-3) between active and placebo, and then pooling the placebo subjects together for comparison. In Cohort 4, a 2:1 randomization ratio will be used together with a strategy that allows for a proportion of placebo participants from Cohorts 1-3 to be borrowed using a matching algorithm to increase power while also minimizing the proportion of placebo participants.

4.7.2. Dose Rationale

The study is designed to evaluate the efficacy of EDP1815 in the treatment of atopic dermatitis at three different doses across two regimens, 8.0×10^{10} total cells QD, 1.6×10^{11} total cells QD, 3.2×10^{11} total cells BID and 6.4×10^{11} total cells QD.

The pharmacological site of action of EDP1815 is within the epithelium of the small intestine where EDP1815 interacts with immune and epithelial cells. These interactions modify the systemic immune system and promote inflammation resolution throughout the body. The preclinical and clinical data generated to date suggest this is a broad effect working across Th1, Th2 and Th17 pathologies. As the intent is to generate a maximal inflammation-resolving phenotype regardless of inflammation pathology, the dose response is expected to be common across indications, and therefore we aim to cross compare to previous studies to support this hypothesis. A full dose-ranging study is currently being carried out in a phase 2 study (EDP-1815-201) in psoriasis patients.

Evelo's Phase 1 Study EDP1815-101 evaluated EDP1815 for the treatment of atopic dermatitis with an oral dose of 8.0×10^{11} cells delivered as ten capsules once a day for 8 weeks. This dose was safe and well tolerated and clinical benefit was observed with an improvement of 50-65% over placebo by Week 8 in EASI, SCORAD, and vIGA*BSA endpoints. In addition, doses of 1.6×10^{11} and 8.0×10^{11} total cells given for 28 days have been investigated in this study for the treatment of psoriasis. Similar clinical benefit was observed at both dose levels. A Phase 2 dose ranging study in psoriasis (EDP1815-201) was conducted in approximately 225 participants for 16 weeks, at doses of 8.0×10^{10} , 3.2×10^{11} , and 8.0×10^{11} total cells. No evidence of dose response was seen in this study. Further information on these studies is detailed in the EDP1815 Investigator's Brochure (IB).

The doses selected for evaluation in EDP1815-207 represent commercially acceptable dosing regimens in terms of capsule load and frequency for patients. The doses of 8.0×10^{10} total cells and

1.6×10^{11} total cells are comparable with data being generated in the lower dose cohorts of EDP1815-201, whilst the dose of 6.4×10^{11} total cells approximates to that administered in EDP1815-101, cohort 7. This latter total daily dose is being tested as both a once daily and twice daily regimen, to explore whether this leads to a change in the efficacy profile of EDP1815 in atopic dermatitis.

5. SELECTION AND WITHDRAWAL OF PARTICIPANTS

Participants with a confirmed diagnosis of mild, moderate or severe atopic dermatitis will be treated in this study only if they meet all inclusion and no exclusion criteria during screening. Any participant who signs the informed consent form will be considered enrolled in the study. Study screening procedures will begin after participants sign the informed consent.

5.1. Inclusion criteria

To be eligible to participate in this study, all of the following criteria must be met:

1. Must have given written informed consent (signed and dated) and any authorizations required by local law and be able to comply with all study requirements.
2. Males or females aged ≥ 18 and ≤ 75 years old at the time of informed consent.
3. A diagnosis of atopic dermatitis (AD) meeting Hanifin and Rajka criteria for AD at screening ([Appendix 14.1](#)) with patient- or clinician- reported disease duration of at least 6 months.
4. Have severity of atopic dermatitis meeting the below criteria at both Screening and Day 1:
 - i. An IGA of 2, 3 or 4 on the vIGA scale, and;
 - ii. A BSA of $\geq 5\%$, and;
 - iii. An EASI score of ≥ 6 .

A cap will be set for each of the three IGA severity grades. When this cap is reached, Sponsor will notify sites that participants with severity score at Screening and/or Day 1 matching the closed stratum should be considered ineligible according to Inclusion Criterion 4i.

5. All participants must agree to use a bland additive-free, sodium lauryl sulfate (SLS)-free, and fragrance-free emollient cream, gel or ointment twice daily (or more, as needed) for at least 14 consecutive days immediately prior to randomization and must continue this treatment twice daily throughout the trial. See [Section 6.9.1.1. Background Therapy](#).
6. Meet the following contraception criteria:
 - i. Male participants:
 - i. A male participant must agree to use contraception as detailed in [Appendix 14.3](#) of this protocol during their participation in this study and for a period of 90 days after the last dose and refrain from donating sperm during this period.
 - ii. Female participants:
 - i. A female participant is eligible to participate if she is not pregnant, not breastfeeding, and at least 1 of the following conditions applies:
 1. Not a WOCBP as defined in [Appendix 14.3](#) or
 2. A WOCBP who agrees to follow the contraceptive guidance in [Appendix 14.3](#) during their participation in this study, 28 days prior to the first dose and for at least 1 complete menstrual cycle (≥ 30 days) after the last dose.

Agrees to not increase their usual sun exposure significantly during the study.

5.2. Exclusion criteria

Participants are not permitted to enroll in the study if any of the following criteria is met:

1. Atopic dermatitis limited to the hands and/or feet and/or scalp.
2. Have been in a clinical trial for EDP1815 prior to signing of ICF.
3. History of active skin infection within 14 days prior to randomization.
4. Evidence of dermatologic conditions that may, in the opinion of the investigator, interfere with AD evaluation or the assessment of treatment response.
5. Use of phototherapy or tanning beds; systemic medications/treatments that could affect AD or its symptoms including immunosuppressive therapy (e.g., oral or injectable corticosteroids, methotrexate, azathioprine, cyclosporine, mycophenolate mofetil, JAK inhibitors, tacrolimus, and/or leukotriene inhibitor) within 4 weeks of randomization.
6. Previously received any biologic agent for AD and either was:
 - a. Unresponsive to biologic agent, or
 - b. Responsive to biologic agent and received this therapy within 3 months or 5 half-lives prior to randomization, whichever is longer.
7. Treatment with topical agents that could affect atopic dermatitis, including topical corticosteroids, topical calcineurin inhibitors (e.g., tacrolimus or pimecrolimus), or topical PDE-4 inhibitor (e.g., crisaborole) within 14 days prior to randomization.
8. Received any investigational or licensed biologic agent for conditions other than AD:
 - a. Any cell-depleting agent, including rituximab, within 6 months prior to randomization, or until lymphocyte cell counts return to normal, whichever is longer.
 - b. Any other biologic agent, within 3 months or 5 half-lives prior to randomization, whichever is longer.
9. Gastrointestinal tract disease (e.g., short-bowel syndrome, diarrhea-predominant irritable bowel syndrome) that could interfere with GI delivery and transit time.
10. Active inflammatory bowel disease.
11. Ongoing acute or chronic infectious disease. Patients with hepatitis B, hepatitis C, and HIV may be enrolled provided that the disease is adequately controlled and/or is in remission.
12. Has received live or live-attenuated vaccination within 6 weeks prior to Screening or intends to have such a vaccination during the study. Non-live and non-replicating vaccines are permitted.

13. Clinically significant abnormalities in screening laboratory values that in the opinion of the Investigator would make a participant unsuitable for inclusion in the study. One retest is permitted within the 28-day screening window.
14. Screening Labs: For women, serum creatinine ≥ 125 $\mu\text{mol/L}$ (1.414 mg/dL); for men, serum creatinine ≥ 135 $\mu\text{mol/L}$ (1.527 mg/dL).
15. Screening Labs: ALT or AST $>2 \times$ ULN.
16. History of clinically significant acute cardiac or cerebrovascular event within 6 months of signing ICF (includes stroke, transient ischemic attack, and coronary heart disease [angina pectoris, myocardial infarction, heart failure, revascularization procedures]).
17. History of active substance (drug and/or alcohol) abuse within the prior 12 months. This does not include the current or prior use of cannabis.
18. In the opinion of the Investigator, evidence of clinically important cardiac conduction abnormalities as judged by the screening ECG.
19. Hypersensitivity to *P histicola* or to any of the excipients.
20. Active mental or psychiatric disorder, which, in the opinion of the Investigator or Sponsor, would make the participant unsuitable for inclusion or could interfere with the participant participating in or completing the study.
21. Recent major surgery within 3 months of signing the ICF, or major surgery planned during the study.
22. Malignancy within 5 years of signing the ICF, except for basal or squamous cell carcinoma of the skin or carcinoma in situ of the cervix that has been successfully treated.
23. Treatment with another investigational drug or device within 3 months or 5 half-lives of investigational agent prior to randomization, whichever is longer.
24. Treatment with supplements containing high doses of probiotics and prebiotics as usually found in capsules/tablets/powders, within 14 days prior to randomization and throughout the study period. Note that probiotic and prebiotic foods that contain low doses are allowed (e.g., yoghurt, kefir, kombucha).
25. Unwillingness to comply with study procedures, including follow-up, as specified by this protocol, or unwillingness to cooperate fully with the Investigator.
26. Have any serious conditions that would be anticipated to require the use of systemic corticosteroids or otherwise interfere with study participation or require active frequent monitoring (e.g., unstable chronic asthma).

27. Have any other conditions, which, in the opinion of the Investigator or Sponsor, would make the participant unsuitable for inclusion or could interfere with the participant participating in or completing the study.

5.3. Screen Failures

Screen failures are defined as participants who consent to participate in the clinical study but are not subsequently randomly assigned to study intervention/entered in the study due to failure to meet eligibility criteria or failing to randomize for any reason. A minimal set of screen failure information is required to ensure transparent reporting of screen failure participants to meet the Consolidated Standards of Reporting Trials (CONSORT) publishing requirements and to respond to queries from regulatory authorities. Minimal information includes informed consent, demography, screen failure details, eligibility criteria, and any AEs and SAEs.

5.3.3. Rescreening

Participants who fail to satisfy inclusion and exclusion criteria at Screening may be rescreened one additional time with the agreement of the Medical Monitor before re-screening.

A participant that is re-screened will be assigned a new participant identifier (ID). Additional information on rescreening will be provided in the appropriate specific user manual.

5.4. Discontinuation from Treatment and/or Withdrawal

Participants may discontinue from treatment and withdraw their participation from the study at any time and for any reason without prejudice to their future medical care by the Investigator or at the study site. Every effort should be made to keep participants in the study. The reasons for participants discontinuing treatment and withdrawing from the study will be recorded in the source files and on the eCRF.

Interruption of treatment is defined as a temporary stopping of IMP that resumes during the treatment period, due to an AE or any other reason. The maximum permitted interruption at one time is 7 days and the participants should not interrupt IMP for more than 14 days in total.

Early discontinuation of treatment is defined as permanent stopping of IMP before the Week 16 visit. Investigators will strive to ensure that a participant who has interrupted treatment for a particular reason will not discontinue IMP unless discontinuation is medically imperative in the Investigator's judgment. However, a dose interruption of more than 7 days or multiple dose interruptions totaling more than 14 days will result in mandatory discontinuation of IMP and early termination of the participant.

Early withdrawal from the study is defined as failing to complete the 16-week treatment and the 4-week follow-up period unless the participant transitions to the Open Label Extension (OLE) Protocol at Week 16.

A participant will discontinue IMP and be withdrawn from the study for any of the following reasons:

1. The participant experiences treatment failure, demonstrated by the participant commencing phototherapy, an oral agent, biological, or intermediate or high-potency topical therapy other than those permitted as rescue therapy.
2. The participant has a serious or intolerable AE that in the Investigator's opinion requires discontinuation from IMP and withdrawal from the study.

NB: Dosing may be interrupted at the Investigator's discretion due to AE or intercurrent illness for a period of up to 7 days, following which the participant may resume treatment if the Investigator considers it safe to do so. The participant should discontinue treatment permanently if the same AE which caused dose interruption occurs a second time requiring another dose interruption and is believed to be related to treatment.

3. The participant has symptoms or an intercurrent illness not consistent with the protocol requirements or that justifies withdrawal.
4. The participant is lost to follow-up.
5. Other reasons (e.g., pregnancy, development of contraindications to use of IMP).
6. The participant withdraws consent, or the Investigator or Sponsor decides to discontinue the participant's participation in the study.

A participant may discontinue IMP and be withdrawn from the study for any of the following reasons:

1. The participant is noncompliant with the protocol.
2. The participant has laboratory safety results that reveal clinically significant hematological or biochemical changes from the baseline values.
3. If the participant is required to start therapy for a concurrent condition that may affect the study endpoints, e.g., a disease modifying agent for asthma.

Investigators should contact the Medical Monitor, whenever possible, to discuss the treatment discontinuation and withdrawal of a participant in advance of this decision.

Investigators should attempt to obtain information on participants in the case of treatment discontinuation and withdrawal. All results of these evaluations and observations, together with a narrative description of the reason(s) for removing the participant, must be recorded in the source documents. The CRF must document the primary reason for treatment discontinuation and withdrawal.

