4.5. Schedule of Study Assessments

Table 4-1: Schedule of Assessments

Procedure	Screening	Treatment Period							Week 20 Visit	Early Termination Visit ^a	ET Follow- Up Phone Call ^a	Rescue Therapy Unscheduled Visit ^b
		1	15	29	57	85	113	141				
Day	-28 to -1	1	15	29	57	85	113	141				
Week	-4 to -1	0	2	4	8	12	16	20				
Visit window (days)	--	--	+/-3	+/-3	+/-3	+/-3	+/-3	+3		+ 3		
Informed consent ^c	X											
Inclusion and exclusion criteria	X	X ^d										
Demography	X											
Medical history and current medical conditions (including smoking status) ^e	X											
Full physical examination ^f	X	X					X		X			
Brief physical examination ^f			X	X	X	X		X				
Height ^g	X											
Weight ^g	X	X		X			X	X	X			
Pregnancy test ^h	X	X		X	X	X	X	X	X			
12-lead ECG ⁱ	X			X			X	X	X			
Laboratory assessments (hematology including eosinophils, biochemistry, urinalysis)	X	X ^d	X	X	X	X	X	X	X			
OPTIONAL Biomarker (blood) collection: DNA Collection		X										
Biomarker (blood) collection: Inflammation immune surveillance in circulation		X	X				X	X	X			

Procedure	Screening	Treatment Period							Week 20 Visit	Early Termination Visit ^a	ET Follow- Up Phone Call ^a	Rescue Therapy Unscheduled Visit ^b
		1	15	29	57	85	113	141				
Day	-28 to -1	1	15	29	57	85	113	141				
Week	-4 to -1	0	2	4	8	12	16	20				
Visit window (days)	--	--	+/-3	+/-3	+/-3	+/-3	+/-3	+3		+ 3		
Biomarker (blood) collection: Immune protein markers		X					X		X			
Biomarker (fecal) collection: Microbiome sample**		X										
Vital signs ^j	X	X	X	X	X	X	X	X	X			
Randomization		X ^k										
Dosing ^l		X										
Dispense IMP		X	X	X	X							
IMP accountability / Collect empty wallets/cartons				X		X	X		X			
Digital photography ^m		X		X		X	X	X	X			
vIGA ⁿ	X	X	X	X	X	X	X	X	X		X	
BSA involvement (%) ⁿ	X	X	X	X	X	X	X	X	X		X	
EASI ⁿ	X	X	X	X	X	X	X	X	X		X	
SCORAD ⁿ		X	X	X	X	X	X	X	X			
POEM		X	X	X	X	X	X	X	X			
DLQI		X	X	X	X	X	X	X	X			
PP-NRS ^o	X	→							X			
SD-NRS ^p	X	→							X			
SF-12		X		X		X	X	X	X			

[figure not shown]
Procedure	Screening	Treatment Period							Week 20 Visit	Early Termination Visit ^a	ET Follow- Up Phone Call ^a	Rescue Therapy Unscheduled Visit ^b
		1	15	29	57	85	113	141				
Day	-28 to -1	1	15	29	57	85	113	141				
Week	-4 to -1	0	2	4	8	12	16	20				
Visit window (days)	--	--	+/-3	+/-3	+/-3	+/-3	+/-3	+3		+3		
HADS		X		X		X	X	X	X			
ADCT		X		X		X	X	X	X			
AE/SAE review ^d	X	→										
Concomitant medication review	X	→										
Participant diary ^f		X	X	X	X	X	X	X	X	X		

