6.9. Concomitant Medications and Treatments

Throughout the study, the participant may be prescribed concomitant medications or treatments deemed necessary to provide adequate supportive care at the discretion of the Investigator provided that the medications are licensed. However, it is the responsibility of the Investigator to ensure that details regarding the medication are recorded in full in the eCRF.

All concomitant medications and/or treatments received by a participant should be recorded on the appropriate source document and eCRF with the following minimum requirements:

- Drug trade name
- Total daily dose
- Dates of administration
- Reason for use (indication)
- Dosage information (including dose and frequency)

This will include all prescription drugs, herbal products, vitamins, minerals, over-the-counter (OTC) medications, and vaccines. Any changes in concomitant medications also will be recorded

in the participant's eCRF. The participant's dosing diary may contain information relevant to the documentation of changes in concomitant medication.

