6.9.1.2. Rescue Therapy

If required, Investigators may prescribe / recommend prescription of rescue therapy for participants experiencing unacceptable worsening of atopic dermatitis. Additionally, individuals with uncontrolled atopic dermatitis could be at risk for a secondary skin infection. These participants may be prescribed an antimicrobial therapy to treat the infection as detailed below. Rescue therapy use is allowed throughout the entire study. There is no limit on the number of times that topical rescue therapy can be prescribed, although Investigators and participants may wish to consider whether the study is suitable for them if repeated courses are required.

Rescue therapy, including antimicrobial rescue therapy, should be prescribed as detailed below, and any specific deviations should first be discussed with the Medical Monitor. Participants rescued by such topical therapy will continue to take IMP and use of rescue therapy will be documented in the participant eDiary ([Section 6.6.1 eDiary](#)). Of note, Investigators should make every attempt to conduct the following assessments immediately prior to administering any rescue therapy, by use of an unscheduled visit, if needed:

- EASI
- vIGA
- PP-NRS
- AEs
- Concomitant Medications

For non-sensitive body sites:

- Moderate potency (grade IV and V – [Appendix 14.2](#)) topical corticosteroids, twice daily for up to 7 days

For sensitive sites e.g., head and neck:

- Topical tacrolimus (0.1%), topical pimecrolimus (1%) or grade VII topical corticosteroid, twice daily for up to 7 days

If topical rescue therapy fails to control symptoms adequately, then the participant should be considered for alternative systemic therapy or phototherapy by the Investigator/their practitioner, at which point they will be classified as a treatment failure and IMP will be discontinued.

For possible skin infection:

- Topical:
 - Appropriate courses of topical antimicrobial therapies, such as fucidic acid cream (e.g., Fucidin), are acceptable for use for skin infections, as required
 - If requiring concomitant moderate potency steroid therapy, fucidic acid with betamethasone 0.1% (as the valerate ester), (e.g., Fucibet cream) twice daily for up to 7 days
- Oral:
 - Appropriate course(s) of oral antibiotic(s) may be prescribed as per clinical need

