6.9.2.2. Discontinuation of Prohibited Concomitant Medications

Use of any of the following concomitant medications during the study require the concomitant medication to be immediately discontinued where possible. If the prohibited medication cannot be discontinued for any reason, then the IMP should be discontinued:

- Emollients containing additives including SLS
- Topical Corticosteroids or Topical Calcineurin Inhibitors (unless used as Rescue Therapy, [Section 6.9.1.2 Rescue Therapy](#))
- Topical PDE-4 Inhibitors
- Bleach baths
- Tanning beds
- Leukotriene Receptor Antagonists
- Allergen Immunotherapy

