6.9.2.3. Prohibited Concomitant Medications Requiring IMP Discontinuation

Introduction of any of the following concomitant medications during the study will be classified as a treatment failure and require IMP discontinuation:

- Phototherapy treatment
- Systemic treatments that may lead to clinical improvements in atopic dermatitis, e.g., oral or injectable corticosteroids, methotrexate, azathioprine, cyclosporine, mycophenolate mofetil, JAK-inhibitors, biologic therapy, and other systemic immunosuppressive therapy (note single dose intra-articular or intra-lesional corticosteroid therapy is permitted).

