14.2. Classification of Potency of Topical Corticosteroids

Potency	Class	Topical Corticosteroid	Formulation
Ultra high	I	Clobetasol propionate	Cream 0.05%
		Diflorasone diacetate	Ointment 0.05%
High	II	Amcinonide	Ointment 0.1%
		Betamethasone dipropionate	Ointment 0.05%
		Desoximetasone	Cream or ointment 0.025%
		Fluocinonide	Cream, ointment or gel 0.05%
		Halcinonide	Cream 0.1%
		Betamethasone dipropionate	Cream 0.05%
Moderate	III	Betamethasone valerate	Ointment 0.1%
		Diflorasone diacetate	Cream 0.05%
		Triamcinolone acetonide	Ointment 0.1%
		Desoximetasone	Cream 0.05%
		Fluocinolone acetonide	Ointment 0.025%
		Fludroxycortide	Ointment 0.05%
		Hydrocortisone valerate	Ointment 0.2%
		Triamcinolone acetonide	Cream 0.1%
Low	V	Betamethasone dipropionate	Lotion 0.02%
		Betamethasone valerate	Cream 0.1%
		Fluocinolone acetonide	Cream 0.025%
		Fludroxycortide	Cream 0.05%
		Hydrocortisone butyrate	Cream 0.1%
		Hydrocortisone valerate	Cream 0.2%
		Triamcinolone acetonide	Lotion 0.1%
		Betamethasone valerate	Lotion 0.05%
		Desonide	Cream 0.05%
		Fluocinolone acetonide	Solution 0.01%
	VII	Dexamethasone sodium phosphate	Cream 0.1%
		Hydrocortisone	Lotion, cream, or ointment 2.5%
		Hydrocortisone acetate	Cream 1%
		Methylprednisolone acetate	Cream 0.25%

Source: WHO (1997) and Tadicherla et al 2009

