5.3.2.3 Prohibited Concomitant Medications

The following medications are not allowed at any point during the study:

- Live (attenuated) vaccinations (a non-replicating / non-live vaccine when the first dose of IMP was not taken within a 7-day window of the administration of vaccine is allowed).

Type 1 prohibited medications are prohibited concomitant medications which may affect efficacy requiring the concomitant medication to be immediately discontinued where possible once the use is discovered. If the prohibited medication cannot be discontinued for any reason, then the IMP should be discontinued:

- Emollients containing additives including SLS.
- Topical Corticosteroids (TCS) or Topical Calcineurin Inhibitors (TCI) (unless considered a rescue therapy).
- Topical PDE-4 Inhibitors.
- Bleach baths.
- Tanning beds.
- Leukotriene Receptor Antagonists.
- Allergen Immunotherapy.

Type 2 prohibited medications are prohibited concomitant medications which may affect efficacy requiring IMP discontinuation:

- Phototherapy treatment
- Systemic treatments that may lead to clinical improvements in atopic dermatitis, e.g., oral or injectable corticosteroids, methotrexate, azathioprine, cyclosporine, mycophenolate mofetil, JAK-inhibitors, biologic therapy, and other systemic immunosuppressive therapy (note single dose intra-articular or intra-lesional corticosteroid therapy is permitted).

If a prohibited medication is found to have been used, this will be captured into the protocol deviations log.

Prohibited medications will be identified by the sponsor in a separate spreadsheet.

Any medications taken during the study and classified as type 1 prohibited medications in the spreadsheet will be considered as type 1 prohibited medications with exception for

1. Medications which stopped at least 14 days before Day 1
2. Medications which started strictly before screening and carried on throughout study to week 16
3. Medications which are emollients and started on or after screening, but before Day 1
4. Medications which are emollients and started before screening and stopped before Day 1

Any medications taken during the study and classified as type 2 prohibited medications in the spreadsheet will be considered as type 2 prohibited medications with exception for medications which stopped at least 14 days before Day 1.

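### Protocol 5.4 item 1 withdraws a participant for starting a stronger non-rescue topical, while 6.9.2.2 only stops the topical; for early use, Week 16 responder status can depend on which rule the site followed

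*Protocol*

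**What the plan says.** **Protocol 5.4, item 1.** Treatment failure is on the list of mandatory reasons for stopping study drug and leaving the study. It is shown by "commencing phototherapy, an oral agent, biological, or intermediate or high-potency topical therapy other than those permitted as rescue therapy". There is no exception for a topical that is then stopped.

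**Protocol 6.9.2.2.** The list covers topical corticosteroids and calcineurin inhibitors not used as rescue, at any potency. The medication is to be stopped at once where possible. "If the prohibited medication cannot be discontinued for any reason, then the IMP should be discontinued". Withdrawal from the study is not mentioned.

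**Protocol 6.9.2.3.** Phototherapy and systemic treatments are the only entries that "will be classified as a treatment failure and require IMP discontinuation". Topicals are not listed.

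**Protocol 6.9.1.2.** If topical rescue is not enough, treatment failure arises when systemic therapy or phototherapy is considered. For departures from the rescue rules, "any specific deviations should first be discussed with the Medical Monitor".

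**SAP.** Section 5.3.2.3 repeats the 6.9.2.2 list as type 1 prohibited medication, and "Prohibited medications will be identified by the sponsor in a separate spreadsheet". Section 13 records that type 1 use is handled like rescue use. In Table 1 (section 9.3.1), Week 16 data are used as collected when last use was 28 days or more before the visit. Section 7.1.2 counts withdrawal for treatment failure as related to study medication, and section 7.1.2.1 scores a response missing for that reason as non-response.

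**The concern.** The two protocol rules overlap for a non-rescue steroid of more than low potency, and they prescribe different actions. One removes the participant; the other keeps the participant on study drug once the topical is stopped. A site cannot follow both.

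The site's choice can reach the primary estimand. A participant who used such a topical early, stopped it and went on to respond would be counted in opposite ways under the two rules. Under 5.4, a Week 16 assessment that the SAP would have used is also never made. Later review of withdrawal reasons or central classification of drugs cannot recreate that visit.

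**Working it through.** The plan gives no figure on this point, so there is none to reproduce. The check follows one participant through both rules and then sizes one event.

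**1. Which rule is the outlier**

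| Source | Non-rescue stronger topical, started then stopped |
|---|---|
| Protocol 5.4 item 1 | Treatment failure: stop study drug and withdraw |
| Protocol 6.9.2.2 | Stop the topical; study drug continues |
| Protocol 6.9.1.2 | Treatment failure tied to systemic therapy or phototherapy |
| Protocol 6.9.2.3 | Treatment failure tied to phototherapy or systemic treatment |
| SAP 5.3.2.3, 9.3.1 and 13 | Type 1: handled like rescue use |

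Only 5.4 item 1 treats the topical itself as treatment failure.

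**2. Where the routes part in EDPS1**

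The SAP boundary is last use 28 days before the actual Week 16 visit. Table 4-1 puts that visit at Day 113 ± 3.

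- Nominal boundary: 113 − 28 = Day 85.
- Earliest visit: 110 − 28 = Day 82. Latest visit: 116 − 28 = Day 88.
- Protocol 7.7 places the visit 113 days after Day 1, literally Day 114, which moves each boundary one day later. SAP 7.7 also keeps out-of-window visits, so the actual visit date decides.

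**3. Example.** A non-rescue high-potency steroid is used on Days 20–24 and stopped. The participant would meet EASI-50 at Week 16. Last use is 113 − 24 = 89 days before the visit, so the 28-day condition is met.

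- *Under 5.4:* the participant is withdrawn for treatment failure, a related reason (SAP 7.1.2). Week 16 is missing and scored as non-response (SAP 7.1.2.1). The Early Termination visit does not stand in for it (SAP 7.7). Related discontinuation has priority among intercurrent events (SAP 9.3.1), so the type 1 label does not reverse this. Result: **non-responder**.
- *Under 6.9.2.2:* study drug continues, Week 16 is attended and the data are used as collected. Result: **responder**.

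**4. Where the routes agree**

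- Last use less than 28 days before Week 16: non-response by either route.
- The participant would not have responded: non-response by either route.
- EDPS6 (SAP 7.1.2.6): any type 1 use since Day 1 gives non-response, as does related withdrawal, so the route makes no difference.

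**5. Size of one event.** Protocol 11.8 plans on 58 evaluable participants per group. A withdrawn participant scored as a non-responder stays in the denominator, so one event changes the arm's rate by 1/58 = 0.0172, or 1.7 percentage points, if the participant would have responded, and by 0 otherwise.

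The documents do not say how often such events occur, so the total cannot be calculated.

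**The case against.** The best defence is that the two sections describe different events. Section 5.4 speaks of a participant who experiences treatment failure, with the new therapy as evidence of it; 6.9.2.2 speaks of a listed product that is used and then stopped. The Early Termination text in 7.9 ties a treatment-failure visit to the start of AD therapy, which suits deliberate escalation. Section 5.4 also asks for every effort to keep participants in the study, and investigators should contact the Medical Monitor before a withdrawal whenever possible.

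This reading is possible, and these controls should reduce variation between sites. But neither document draws the line between escalation and incidental use, and under 5.4 starting the topical is itself the proof of failure. Neither general encouragement nor a consultation where possible ranks the rules. Prior discussion with the Medical Monitor would also miss self-treatment.

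A second objection is that planned analyses already test the result. This largely stands. EDPS6 does not depend on the route and is marked for the top-level results (SAP 15.2.1). EDPS4 leaves related withdrawals missing, which checks the non-response scoring from another side.

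A third is that consistency could be reached the other way, by moving these topicals into 6.9.2.3 and SAP type 2. That would be coherent and more conservative. It would, however, change the sections that already agree and lose Week 16 data that the SAP would use. It would also keep a potency criterion whose term, intermediate, is not a grade in Appendix 14.2 ("Classification of Potency of Topical Corticosteroids").

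A reader might infer a loss of power. The documents do not support that. Any such figure needs an assumed event frequency. The 25% and 50% planning rates are stated for the primary endpoint, so deducting non-responders from them again may count them twice. Nor do the documents support inferring bias towards either arm: treatment is blinded within cohort, and nothing suggests that the events differ by arm.

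**Conclusion.** The inconsistency is real and minor. Protocol 5.4 item 1 conflicts with 6.9.2.2 for a stronger non-rescue topical that is started and then stopped, and it stands apart from 6.9.1.2, 6.9.2.3 and the SAP.

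In EDPS1 the consequence is confined to participants whose last use was at least 28 days before the actual Week 16 visit, who were withdrawn under 5.4, and who would have responded. Each costs up to 1.7 points of one arm's rate, on the planned 58 evaluable per group. The number of such participants is unknown, no imbalance between arms is shown and no power loss is claimed. The overall effect is probably small. The case for acting is that the change is cheap and would prevent avoidable loss of primary endpoint data.

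**What to change.** 1. Amend Protocol 5.4 item 1 so that treatment failure means the therapies listed in 6.9.2.3, with a cross-reference sending non-rescue topicals to 6.9.2.2. A participant who stops the topical then continues study drug and attends Week 16.
2. Leave the existing withdrawal rule unchanged for those whose study drug must be discontinued. Section 5.4 couples discontinuation with withdrawal, and keeping such participants on study would be a larger change.
3. Report, by arm and cohort, the number already withdrawn under 5.4 for a topical. The withdrawal reason and the sponsor's type 1/type 2 classification should identify them.
4. If the amendment reaches only Cohort 4, the same early use could count as response there and as non-response in Cohorts 1–3. Cohort 4 borrows 35 placebo participants from Cohorts 1–3 and is compared with Cohort 1 active (SAP Addendum 4.1 and 4.3.2). Read those comparisons alongside EDPS6, and read the matched-placebo comparison also alongside the Cohort 4-only placebo comparison (Addendum 4.3.3.1).

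**Cost.** One amended item with a cross-reference, a clarification to sites and one count. No new analysis rule is needed, because type 1 use is already covered. No potency coding is needed either; the minimum medication fields in Protocol 6.9 do not include potency.

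**Downside.** Retained participants rely on the existing 28-day rule to limit steroid carry-over, and Week 16 visits already lost cannot be recovered.
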